**Major Access-Related Non-Vascular Complications****One of the following:**

- Non-vascular structure, non-cardiac structured perforation, injury, or infection resulting in death, VARC type  $\geq 2$  bleeding, irreversible nerve injury or requiring unplanned surgery or percutaneous intervention
- Non-vascular access site (e.g. trans-apical left ventricular) perforation, injury, or infection resulting in death, VARC type  $\geq 2$  bleeding, irreversible nerve injury or requiring unplanned surgery or percutaneous intervention

**Minor Access-Related Non-Vascular Complications****One of the following:**

- Non-vascular structure, non-cardiac structured perforation, injury, or infection not resulting in death, VARC type  $\geq 2$ , irreversible nerve injury, or requiring unplanned surgery or percutaneous intervention
- Non-vascular access site (e.g. trans-apical left ventricular) perforation, injury, or infection not resulting in death, VARC type  $\geq 2$  bleeding, irreversible nerve injury or requiring unplanned surgery or percutaneous intervention

aAny complication related to the device insertion, delivery, and complete removal of all its components (delivery catheter, sheath, guide wire), excluding the actual implantation in the heart.

bAny device-related vascular access site and any other accessory access sites (venous or arterial) used during procedure.

[figure not shown]
cA failure to achieve haemostasis at the access site, resulting in alternative treatment (other than manual compression or planned adjunctive endovascular balloon inflation).

[figure not shown]
dIncluding, but not limited to, the lung (e.g. pneumothorax), direct nerve injury, access site or wound infection, mediastinitis, sternal instability, wound dehiscence, and inability to close the chest.

## Appendix C. NYHA Functional Classification

Class I	Patient has cardiac disease but without resulting limitations of ordinary physical activity. Ordinary physical activity (eg, walking several blocks or climbing stairs) does not cause undue fatigue, palpitation, dyspnea, or anginal pain. Limiting symptoms may occur with marked exertion.
Class II	Patient has cardiac disease resulting in slight limitation of ordinary physical activity. Patient is comfortable at rest. Ordinary physical activity such as walking more than 2 blocks or climbing more than 1 flight of stairs results in limiting symptoms (eg, fatigue, palpitation, dyspnea, or anginal pain).
Class III	Patient has cardiac disease resulting in marked limitation of physical activity. Patient is comfortable at rest. Less than ordinary physical activity (eg, walking 1 to 2 level blocks or climbing 1 flight of stairs) causes fatigue, palpitation, dyspnea, or anginal pain.
Class IV	Patient has dyspnea at rest that increases with any physical activity. Patient has cardiac disease resulting in inability to perform any physical activity without discomfort. Symptoms may be present even at rest. If any physical activity is undertaken, discomfort is increased.

### 1.0 SYNOPSIS OF STUDY DESIGN

### 1.1 **Purpose of the Statistical Analysis Plan**

This statistical analysis plan (SAP) is intended to provide a detailed and comprehensive description of the planned methodology and analysis to be used for Portico Valve-in-Valve Retrospective Registry clinical investigation plan (CIP)

### 1.2 **Clinical Investigation Objectives**

The objective of this data-collection study is to evaluate the safety and clinical performance of the Portico transthoracic aortic valve (sizes 23-29 mm) for Valve-in-Valve (ViV) treatment of a failed aortic surgical bioprosthetic valve in patients who are considered at increased surgical risk for a redo surgical aortic valve replacement.

#### 1.3 **Clinical Investigation Design**

This is a multi-center, international, single-arm, retrospective data-collection study. The study will use a Core Laboratory for echocardiogram analysis and a Clinical Events Committee (CEC). The study includes the primary study arm and an exploratory registry arm; both study arms will follow all timepoints and data-collection requirements outlined in Figure 2 of the CIP. This study may include up to 100 patients for the primary analysis population.

Patients must have met the sizing requirements of the PorticoTM transthoracic aortic valve sizing specification ( $\geq$ 19 mm and  $\leq$ 27 mm). Patients must meet all inclusion and exclusion criteria to be eligible for enrollment.

In addition, an exploratory registry arm will collect data for patients that were treated for a failed surgical bioprosthetic aortic valve true inner diameter size of <19 mm or >27 mm. There will be no enrollment limit in the exploratory registry arm.

### 1.4 Endpoints

#### 1.4.1 **Primary Safety Endpoint**

Composite of all-cause mortality, disabling stroke, life threatening bleeding requiring transfusion, Acute Kidney Injury (AKI) requiring dialysis, and major vascular complications at 30 days.

### 1.4.2 Primary Performance Endpoint

Composite of all-cause mortality or disabling stroke at 1 year.

#### 1.4.3 **Descriptive Endpoints**

1. Procedure success defined as:

- Absence of procedural mortality AND
- Successful access, delivery of the valve, and retrieval of the delivery system
- 2. Evaluation of adverse event rates At 30 days and one year:
  - All-cause mortality
  - Cardiovascular-related mortality
  - All Stroke (by severity)
  - Transient Ischemic Attacks (TIA)
  - Myocardial infarction (MI)
  - New pacemaker implant (PPI)
  - Coronary obstruction

#### At 30 days:

- Minor, Major, and Life-threatening bleeding
- Major vascular, major non-vascular access-related, or cardiac structure complication
- Acute Kidney Injury (AKI) stages 1-4

3. Evaluation of adverse event rates annually through 5 years:

- All-cause mortality
- Cardiovascular-related mortality
- All Stroke (by severity)
- TIA

The following will be collected if standard of care or if available:

4. Echocardiographic assessment of valve performance at discharge, 30 days, 1 year, and annually through 5 years including:

- Transvalvular mean gradient
- Indexed Effective orifice area (iEOA)
- Doppler velocity index (DVI)
- Aortic Valve Area (AVA)
- Non-structural valve dysfunction:
  - Prosthetic patient mismatch (PPM) per body mass index (BMI)
  - Degree of aortic valve regurgitation (transvalvular and paravalvular leak (PVL)) as none/trace, mild, mild-moderate, moderate, moderate/severe, or severe per VARC-3; and per VARC-2 none/trace, mild, moderate, or severe).
- 5. Valve Integrity at 1 year and annually through 5 years as assessed by:

• Structural Valve Deterioration (SVD) (by hemodynamic valve deterioration (HVD) stages 1-3 per VARC-3)

Confirmed intrinsic permanent changes to the prosthetic valve, including:

- Wear and tear
- Leaflet disruption
- o Flail leaflet
- Leaflet fibrosis and/or calcification
- Strut fracture or deformation
- Non-structural Valve Dysfunction other than PVL and PPM (HVD stages 1-3 per VARC-3) Any abnormality not intrinsic to the prosthetic valve resulting in valve dysfunction other than PVL and PPM, including:
  - Leaflet entrapment by pannus or tissue
  - Inappropriate positioning or sizing
  - $\circ$  Embolization
- Clinically Significant Thrombosis
  - Meeting either of the following criteria:
    - Clinical sequelae of thromboembolic event or worsening AS/transvalvular AR and HVD Stage 2-3 or confirmatory imaging of thrombosis
      - Or
    - o In the absence of clinical sequelae, both HVD Stage 3 and confirmatory imaging
- Endocarditis (by HVD stages 1-3 per VARC-3) Meeting at least one of the following criteria:
  - Fulfilment of the Duke endocarditis criteria
  - Evidence of abscess, pus, or vegetation confirmed as secondary to infection by histological or microbiological studies during re-operation
  - Evidence of abscess, pus or vegetation confirmed on autopsy.

The following definitions of HVD Stages (1-3) will be used when assessing valve integrity.

- Stage 1 (Morphological Valve Deterioration): Evidence of SVD, non-structural valve dysfunction (other than paravalvular or PPM), thrombosis or endocarditis without significant hemodynamic changes.
- Stage 2 (Moderate hemodynamic valve deterioration): Increase in mean transvalvular gradient ≥10 mmHg resulting in mean gradient ≥20 mmHg with concomitant decrease in EOA ≥0.3 cm^2 or ≥25% and/or decrease in Doppler velocity index ≥0.1 or ≥20% compared with echocardiographic assessment performed 1-3 months post-procedure, OR new occurrence or increase of ≥1 graded of intra-prosthetic AR resulting in ≥ moderate AR
- Stage 3 (Severe hemodynamic valve deterioration): Increase in mean transvalvular gradient ≥20 mmHg resulting in mean gradient ≥30 mmHg with concomitant decrease in EOA ≥0.6 cm^2 or ≥50% and/or decrease in Doppler velocity index ≥0.2 or ≥40% compared with echocardiographic assessment performed 1-3 months

post-procedure, OR new occurrence, or increase of ≥2 grades, of intra-prosthetic AR resulting in severe AR.

• Any need for Portico TAVI re-intervention after implant through 5 years

6. Clinical benefit endpoints defined as improvement from baseline to 30 days, 1 year, and annually through 5 years from index procedure, including:

• New York Heart Association (NYHA) functional classification

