**The List of Reportable Events include:**

1. Endpoint VARC-2 and VARC-3 events:
  - Death (all-cause and cardiovascular-related)
  - Myocardial Infarction
  - Major Vascular complications
  - Major non-vascular access-related complications
  - Stroke/TIA
  - Bleeding
  - Acute kidney Injury
  - New permanent pacemaker implantation
  - Coronary obstruction
  - Cardiac structural complication
  - Portico valve endocarditis
  - Portico valve thrombosis
  - Need for reintervention (conversion to surgery or repeat TAVR ViV)
  - Portico valve structural deterioration
2. All non-serious device or procedure related Adverse Events.
3. All Serious Adverse Events (SAEs) regardless of device or procedure relationship
4. All Cardiovascular and Neurological events regardless of device or procedure relationship
5. Device Deficiencies (DDs)/Device Malfunctions

Sites must report SAEs and DDs to the Sponsor no later than 3 calendar days from the day the site personnel became aware of the event or as per the investigative site's local requirements, if the requirement is more stringent than those outlined.

Sites must record the date the study staff became aware that the event met the criteria of an SAE in the source document. The Investigator will further report the SAE to the local EC according to the institution's EC reporting requirements.

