### 12.2.3 Descriptive Endpoints Analyses

Descriptive endpoints are listed in Section 5.3. Study results will be summarized using descriptive statistics including mean, standard deviation, median and range for continuous data and count and percentage for categorical data.

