#### 2.2.3 Survival Analyses

Survival analysis will be conducted to analyze time-to-event variables. Subjects without events will be censored at the time of analysis. Survival curves will be constructed using Kaplan-Meier estimates and Greenwood standard errors.

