### 2.3.2 **Descriptive Endpoints**

Descriptive endpoints are listed in Section 1.4.3. Study results will be summarized using descriptive statistics including mean, standard deviation, median and range for continuous data and count and percentage for categorical data. All analyses will be performed on available data.

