#### 2.8 Handling of Missing Data

All analyses will be performed on available data and additional considerations due to the COVID-19 pandemic are detailed in Section 2.2.4 and in the primary and secondary endpoint sections. This is a retrospective study collecting data that is available per the site standard of care (SOC) and the majority of subjects will be followed for at least 1 year. Therefore, there is no plan to impute missing data.

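### Valve integrity is summarised by yearly crude percentages with no rule for earlier failures, replaced valves or death, so the figures do not estimate cumulative valve failure

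*SAP*

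**What the plan says.** SAP 1.4.3 item 5 lists "Valve Integrity at 1 year and annually through 5 years as assessed by" four failure types: structural valve deterioration by HVD stages 1 to 3, non-structural dysfunction other than leak and mismatch, clinically significant thrombosis, and endocarditis. Items 4 to 6 stand under the condition "The following will be collected if standard of care or if available". Item 5 also lists "Any need for Portico TAVI re-intervention after implant through 5 years".

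The method is in SAP 2.3.2: "count and percentage for categorical data. All analyses will be performed on available data". Protocol 12.2.3 gives the same one, "count and percentage for categorical data". SAP 2.8 adds "Therefore, there is no plan to impute missing data".

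SAP 2.2.3 is generic: "Survival analysis will be conducted to analyze time-to-event variables. Subjects without events will be censored at the time of analysis". It names no endpoint. The only endpoint assigned a Kaplan-Meier analysis is the 1-year composite of death or disabling stroke (SAP 2.3.1.2). Neither document contains a competing-risk method.

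The list of reportable events in protocol 11.6 includes "Portico valve structural deterioration", endocarditis, thrombosis and re-intervention. Non-structural dysfunction is not named there. SAP 3.2 summarises adverse events over all enrolled subjects, and CEC-adjudicated events over all with an implant attempt, as counts and percentages without a time scale. Valve replacement is not among the reasons that end participation in protocol 9.4.

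**The concern.** The item-5 failures are permanent changes or dated events, whereas the stated summary is a percentage at each annual timepoint among subjects with data. A valve that reaches Stage 3 at 18 months and is then replaced may have no Portico echo at year 2. Its recipient may stay in the table with the new valve's echo, drop out of it, or still be counted as a failure. The documents do not say which. A recipient who dies leaves the denominator.

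Five-year valve integrity is the study's main long-term valve outcome. If the year-5 percentage is read as the share of valves that failed within 5 years, it answers a different question. The size and even the direction of the gap then depend on handling rules that the SAP leaves open.

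**Working it through.** The documents state no valve-failure rate, so there is no planned figure to reproduce. The check is an illustration with constant hazards.

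**Inputs**
- Death hazard λ = −ln(0.858) = 0.153 per year, from the 85.8% one-year survival in the valve-in-valve registry cited in protocol 2.1. Holding it constant for 5 years is an assumption. It leaves 0.858^5 = 46% alive at year 5.
- Failure hazard h = 0.02 per year, range 0.01 to 0.04 (assumption).
- Exit rate e = 0, 0.5, 1 or 2 per year (assumption): how fast a failed valve leaves view beyond background death, through replacement, explant or loss from assessment.

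**Cumulative incidence of first failure, death competing**

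CI(5) = h/(h+λ) × [1 − exp(−5(h+λ))]

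For h = 0.02: 0.02/0.173 × [1 − exp(−0.866)] = 0.1155 × 0.579 = 6.7%. For h = 0.01 it is 3.4%, and for h = 0.04 it is 12.8%.

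**Year-5 percentage failed among subjects alive with a Portico in view**

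Ratio of failed to intact: g = h/(e−h) × [1 − exp(−5(e−h))]. Percentage = g/(1+g). The death hazard cancels because it is the same in both groups.

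For h = 0.02 and e = 1: g = 0.02/0.98 × [1 − exp(−4.9)] = 0.0203, which gives 2.0%.

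| h per year | CI at 5 years | e = 0 | e = 0.5 | e = 1 | e = 2 |
|---|---|---|---|---|---|
| 0.01 | 3.4% | 4.9% | 1.8% | 1.0% | 0.5% |
| 0.02 | 6.7% | 9.5% | 3.7% | 2.0% | 1.0% |
| 0.04 | 12.8% | 18.1% | 7.3% | 4.0% | 2.0% |

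At h = 0.02 the visit percentage runs from 85% too low (1.0/6.7) to 42% too high (9.5/6.7).

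**Course over time, h = 0.02 and e = 1**

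| Year | 1 | 2 | 3 | 4 | 5 |
|---|---|---|---|---|---|
| Visit percentage | 1.3 | 1.7 | 1.9 | 2.0 | 2.0 |
| Cumulative incidence | 1.8 | 3.4 | 4.7 | 5.8 | 6.7 |

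The visit figure levels off while failures go on accumulating.

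**Second model.** This one has a separate state for replaced valves and doubles the death hazard after failure. With death 0.153, failure 0.05 and replacement 0.5 per year, the year-5 visit percentage is 7.3% among original valves in place. It is 6.4% if a replacement valve is scored as intact. Cumulative incidence is 15.7%. With no replacement and no excess death after failure, the visit figure is 22.1%.

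**Sensitivity to the death curve.** The same registry reports 17 of 202 dead by 30 days. Putting that mortality early leaves about 0.07 per year afterwards and moves the 6.7% only to 7.4%.

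**The case against.** The strongest reply is that this is a missing specification, not an established bias. No sentence says that the percentage is taken among those seen at the visit. Item 3 uses similar annual timing for all-cause mortality, which cannot be a percentage of survivors, so the timing phrase alone does not imply a snapshot. The endocarditis definition accepts findings at re-operation or autopsy, and protocol Appendix B classes thrombosis by time of occurrence; both suggest events. All of this stands. The at-visit denominator is an inference from item 5 read with the available-data rule. If it is not what is meant, the SAP simply does not say what is.

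A reader might infer that failed valves vanish from the report. The documents do not support that. Re-intervention is worded through 5 years, most failure types are reportable and enter summaries over all enrolled or attempted subjects, re-intervention details are collected at every visit from discharge (protocol Table 3), and replacement does not end participation. What those summaries lack is a time scale.

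A reader might also infer that the percentage is always too low, or that it falls as more valves fail. The calculation shows neither. With no exit the figure is too high. At a fixed exit rate it rises with the failure rate and never falls from year 1 to year 5.

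The size of the gap comes from the exit rate, which has no source in the documents. A competing-risk curve does not cure echoes that are missing or late either. Both points are fair and limit how far the illustration can be pressed.

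**Conclusion.** The point holds as a gap in the analysis of a descriptive endpoint. The SAP assigns item 5 a crude count and percentage and leaves the denominator, the carry-forward of earlier failures, replaced valves and death undefined. Read naturally, the result is not the cumulative failure rate and can err in either direction: 1.0% to 9.5% at year 5 against 6.7%, at 2% failure and 0.153 deaths per year. The range rests on constant hazards, an assumed failure rate and an assumed exit rate. Only the 85.8% one-year survival comes from the documents. The study is a single-arm registry of up to 100 subjects in its primary population, with no hypothesis test, and its primary endpoints are unaffected. The change is worthwhile because it is cheap, not because a conclusion hangs on it.

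**What to change.** In SAP 2.3.2, for each item-5 failure type (structural deterioration by HVD stage, including Stage 1 as the endpoint states):

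- Report the cumulative incidence of first occurrence at 1, 2, 3, 4 and 5 years, with death without failure as a competing event.
- Censor subjects who have not failed at their last valve assessment, not at the time of analysis as in the generic SAP 2.2.3.
- Keep a failed valve counted after replacement or explant, and do not score a replacement valve's echo as an intact Portico.
- Keep the annual percentages as a supplement, each with the number assessed.

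The cost is SAP wording and programming, with no new visits. There are two downsides. Failures found by echo are dated at the detecting echo, and these echoes are taken only where standard of care provides them. Non-structural dysfunction is not named in the protocol 11.6 list, so its date must come from core-laboratory echo or re-intervention records.

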**Table 3: Data Collection Overview**

Visit Activity or Information Collected	Initial Data Collection			Follow-Up Data Collection					
	Baseline	Procedure	Discharge	30-Day	1 Year	2 Year	3 Year	4 Year	5 Year
Demographics	X								
Medical History	X								
Lab measurements*	X			X					
Clinical Assessment with physical exam ^			X	X	X	X	X	X	X
Cardiovascular Medications (examples: cardiac medications and blood thinners)	X			X	X	X	X	X	X
NYHA Classification β	X			X	X	X	X	X	X
Transthoracic Echocardiography (TTE) or Transesophageal Echocardiography (TEE) γ	X		X	X	X	X	X	X	X
Procedure details		X							
Adverse Events, Device Deficiency, and Withdrawal Σ		X	X	X	X	X	X	X	X
Reintervention Procedure (if applicable)			X	X	X	X	X	X	X
Protocol Deviations related to informed consent process or inclusion/exclusion criteria, or safety reporting requirements (if applicable)	X	X	X	X	X	X	X	X	X

\*Blood tests that are standard of care; βNYHA will be determined from signs and symptoms observed attributed to heart function and can be calculated from medical records. ^Clinical assessment will assess general health and information on any new diagnostics, treatments, or tests since the last visit. ΣIf applicable; γEchocardiograms submitted to the Echo Core Lab should be imaging medium but may be provided as a report if imaging is not available to submit to the core lab.

Note: Neurologic assessments will be collected for any neurologic event (if applicable) and may be assessed from available medical records.

In the event that more than 1 echocardiogram or required data point is performed and available within a specific study data collection timepoint, the data closest to the study timepoints will be used for the primary analysis. However, all available data should be collected in additional applicable CRFs. Additional echocardiograms should be submitted to the echocardiogram core lab for analysis. Data may be collected based on availability from SOC and protocol deviations for out of window/missed visit or out of window/missed data will not be required.

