## 2.0 ANALYSIS CONSIDERATIONS

#### 2.1 Analysis Population

#### 2.1.1 **Primary Analysis Population**

The primary analysis population will include patients who have signed an Informed Consent Form (ICF), or for those patients deceased at the time of study screening, all local and national regulatory requirements were met for consent, and at minimum, the Portico delivery system entered his/her vasculature for an attempted Portico ViV implant. Subjects that are enrolled and later determined to be screen failures (those that do not meet all inclusion criteria or meet any exclusion criteria) will not be included in any analysis. Subjects that are enrolled in the Exploratory Arm of the study will not be included in the primary arm of the study.

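### The NYHA improvement percentage describes assessed survivors only, is not labelled so, and is never set against deaths and missing assessments in one table

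*SAP*

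**What the plan says.** - **Endpoint.** SAP 1.4.3 item 6: "Clinical benefit endpoints defined as improvement from baseline to 30 days, 1 year, and annually through 5 years from index procedure". The only component listed is "New York Heart Association (NYHA) functional classification". Protocol 5.3 says the same. Neither document says how large a change counts as improvement.
- **Summary.** SAP 2.3.2 gives "count and percentage for categorical data" and adds: "All analyses will be performed on available data". No denominator is named, and there is no rule for a subject who died before the visit.
- **Missing data.** SAP 2.8: "Therefore, there is no plan to impute missing data".
- **Collection.** Item 6 stands below the line "The following will be collected if standard of care or if available" in SAP 1.4.3. The notes to Protocol Table 3 add: "Data may be collected based on availability from SOC". They also waive deviation reports for missed visits.
- **Who is in the population.** SAP 2.1.1 makes explicit provision "for those patients deceased at the time of study screening", so some subjects will have died before later visits. Protocol 4.3 asks sites to consider eligible patients whatever their outcome or survival.
- **Who leaves early.** Under Protocol 9.4, a subject whose implant attempt failed completes the study at 30 days.
- **Related reporting.** SAP 1.4.3 items 2 and 3 report all-cause mortality at 30 days, 1 year and yearly to 5 years. SAP 3.3 summarises reasons for early termination, deaths included, at every scheduled visit.

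**The concern.** A subject who has died has no NYHA class at later visits. Under an available-data rule with no imputation, that subject drops out of the percentage. The plan takes care not to select on survival at enrolment, but the one endpoint it calls clinical benefit is then summarised on survivors. Failed implants disappear from the 1- to 5-year figures in the same way, as do living subjects with no recorded class.

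What is at stake is how the number is read. With no test planned, the printed percentage is the result. A reader who sees a clinical-benefit percentage at year 3 may take it to describe everyone treated, when it describes those alive, still followed and assessed.

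**Working it through.** The plan gives no expected NYHA rate, precision or power for this endpoint, so it has no figure to reproduce.

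**Set-up.** Let p be the proportion improved among assessed survivors at a visit, S the proportion of treated subjects alive, and a the proportion of survivors assessed.

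- Available-data percentage = p.
- Alive and improved among all treated, if all survivors are assessed (a = 1) = p × S.
- Ratio = p / (p × S) = 1/S. In a fixed cohort S cannot rise, so the ratio cannot fall.
- Gap in points = p × (1 − S).

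**Inputs.** Protocol 2.1 cites a valve-in-valve registry of 202 patients treated with two other valve types. It reports 17 deaths by 30 days (17/202 = 8.4%, matching the stated figure) and 85.8% survival at 1 year. These serve as illustration only. Not in the documents, and therefore assumed: p = 80%, and yearly mortality after year 1 of 5%, 10% or 15%.

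| Visit | S | 1/S | Available data | Alive and improved | Gap (points) |
|---|---|---|---|---|---|
| 30 days (registry) | 185/202 = 0.916 | 1.09 | 80.0% | 73.3% | 6.7 |
| 1 year (registry) | 0.858 | 1.17 | 80.0% | 68.6% | 11.4 |
| 5 years, 5% a year (assumed) | 0.858 × 0.95⁴ = 0.699 | 1.43 | 80.0% | 55.9% | 24.1 |
| 5 years, 10% a year (assumed) | 0.858 × 0.90⁴ = 0.563 | 1.78 | 80.0% | 45.0% | 35.0 |
| 5 years, 15% a year (assumed) | 0.858 × 0.85⁴ = 0.448 | 2.23 | 80.0% | 35.8% | 44.2 |

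With p from 60% to 90% as well, the 5-year gap runs from 18.1 to 49.7 points. That width shows that the documents do not fix the 5-year size.

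**Does the gap always widen?** The ratio cannot shrink, but the gap in points can if p falls fast enough. From 30 days to 1 year, p would have to fall in relative terms by more than 1 − (1 − 0.916)/(1 − 0.858) = 41% (unrounded inputs).

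**Living subjects with no recorded class.** Let q be the unknown proportion improved among them. Alive and improved is then S × [a × p + (1 − a) × q]. At 1 year with a = 0.90 (assumed) and p = 0.80:

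- q = 0: 0.858 × 0.72 = 61.8%
- q = p: 0.858 × 0.80 = 68.6%
- q = 1: 0.858 × 0.82 = 70.4%

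Missing classes can therefore move the answer in either direction. Counting them as not improved gives the lower bound only.

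**The case against.** The strongest reply is that NYHA class among assessed survivors is a legitimate descriptive summary, and that alive-and-improved is simply a different target. Deaths appear at the same visits under SAP 1.4.3, and terminations under SAP 3.3. The endpoint is one of six descriptive items, and SAP 2.10 plans no hypothesis test even for the primary endpoints. The plan also limits missing classes: NYHA may be derived from medical records (Protocol Table 3 notes), and data may be gathered remotely (Protocol 9).

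Most of this stands. It makes the point minor and means the available-data percentage should stay. It does not close the gap, because the separate tables do not say why subjects are absent from a given NYHA denominator. In particular, a living subject who misses a visit is not withdrawn (Protocol 8.2) and needs no deviation report, so that loss need not appear in the termination table.

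A reader might go further and infer that the plan overstates benefit, or that a stable or rising rate over five years would be produced by survivor selection. The documents do not support either. *Overstated* holds only against a target the SAP never claims to estimate. The calculation above holds p fixed and so does not model selection, which would require that those who die or drop out had improved less often; nothing in the documents shows that. Even the loss of dead subjects from the denominator follows from the available-data rule and is not stated in words.

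**Conclusion.** The point holds as a matter of definition and labelling. As written, the NYHA percentage at each visit covers assessed survivors only, the SAP does not say so, and no planned table joins NYHA with death, failed implant and missing assessment.

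Against alive-and-improved among all treated, the ratio is about 1.09 at 30 days and 1.17 at 1 year. This assumes that every survivor is assessed and that survival resembles the cited registry of other devices. The 5-year ratios of 1.43 to 2.23 rest on assumed mortality and should not be quoted as an expected size. No primary conclusion changes.

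**What to change.** In SAP 2.3.2:

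1. Define improvement, for example at least one NYHA class from baseline. Inclusion criterion 6 requires class II to IV before the procedure, so every eligible subject has room to improve by one class.
2. At each visit, tabulate improved, unchanged, worsened, dead and not recorded over all primary-population subjects past that visit window. Judge *past the window* by time since the procedure, so that subjects who died are counted. From year 1, show exits after an unsuccessful implant as a separate row.
3. Keep the available-data percentage, labelled *among assessed survivors*, with its n.
4. Do not lead with a figure that counts living subjects without a recorded class as not improved. Show that at most as a lower bound.

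The change needs no new data, since deaths, terminations and NYHA class are already collected. The cost is a slightly larger table and a full-population figure that is less favourable than the survivor percentage.
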